### Estimated Study Calendar

Table 2: Milestones

YEAR 1		
Milestones	Description	Approximate Dates
Recruitment and random assignment of participants	Recruitment and random assignment will begin during the second quarter of year one and continue throughout the year.	04/30/2015
Intervention sessions and data collection events completed	The intervention sessions will begin during the second half of year one, with approximately 53 participants from the intervention (plus family participants) and 22 control participants will complete the intervention and pre-post-data collection events.	04/30/2015
YEAR 2		
Recruitment and random assignment of participants.	Recruitment and random assignment will continue through the first half of year two.	10/31/2015
Intervention sessions and data collection events completed	The intervention sessions will continue throughout year two, approximately 110 primary participants (plus family participants) and 50 control participants will complete the intervention and pre-post-data collection events. 6 and 12 month data collection events will be completed for year one participants.	04/30/2016
YEAR 3		
Data analysis	Collaborative analysis of data with stakeholders.	04/30/2017
Collaborative Dissemination	Collaborative dissemination of results back to the community.	04/30/2017

### Study Population

**Recruitment and Consent:** There are ~11,000 Marshallese living in Springdale, Arkansas. Using conservative estimates, 3,000 of the Marshallese living in Springdale, Arkansas have type 2 diabetes, providing a sufficient participant pool for recruitment. Participants will be recruited through the three primary clinics that care for the Marshallese—the Community Clinic (a Federally Qualified Health Center), the Springdale Family Medical Center, and the [name] Clinic in Springdale. In addition, participants will be recruited through local Marshallese churches, community leaders, and Yokwe.net, the primary social media site for the Marshallese community. A more detailed recruitment plan is outlined in the following section. Potential participants will be provided information about the study and given the opportunity to take a brief eligibility screener that determines and documents study eligibility. Up to 300 participants with diabetes (initial participants) will be recruited and enrolled, and each participant in the

Title: *Family Model of DSME in the Marshallese Community*

PI: *[name]*

treatment group will be asked to invite between one and ten family members to attend the diabetes education sessions and potentially join the study. All members of the research team will be trained and certified in participant consent procedures, the study protocol, human subjects protection, and HIPAA regulations. During the presentation/discussion of the study, potential participants will be screened for eligibility. Inclusion/exclusion criteria are as follows:

Initial Participant Inclusion Criteria

- 18 years and older
- Self-reported Marshallese ethnicity or descent
- Self-reported Diabetes Mellitus Type 2 diagnosis by a health care provider

Initial Participant Exclusion Criteria

- Younger than 18 years of age
- Not Marshallese ethnicity or descent
- No reported Diabetes Mellitus Type 2 diagnosis

Family Member Inclusion Criteria

- 18 years and older

Family Member Exclusion Criteria

- Younger than 18 years of age

Potential participants who are interested in joining the study will be provided the opportunity to ask questions, consent and enroll in the study. At enrollment, a participant contact information form will be completed and include participant contact information (phone numbers, address, e-mail), preferred method of contact (i.e. text, phone, mail, e-mail), and demographic information.

**Recruitment Plan.** Identified, recruited, and enrolled: Marshallese recruitment staff will be employed to conduct the study. Participants will be recruited through provider referrals from the three primary clinics that care for the Marshallese: Community Clinic (a Federally Qualified Health Center), the Springdale Family Medical Center, and the [name] Clinic in Springdale. In addition, participants will be recruited through local Marshallese churches, community leaders, our Community Advisory Board, community health events, and Yokwe.net.

In the clinical setting, potential participants who meet the enrollment criteria will be identified by their healthcare provider. All potential participants meeting the inclusion criteria will be systematically provided information about the study and given the opportunity to discuss the study with a Marshallese research staff member. To reduce selection bias and ensure we reach persons who may not have a primary care provider

Title: *Family Model of DSME in the Marshallese Community*

PI: *[name]*

(there is a low rate of insurance and medical homes among the target population), we will also recruit from local Marshallese churches.

For recruitment in the churches, we will distribute recruitment information, which will include the purpose of the study, the PI, sponsor, and inclusion criteria. Study information will be distributed in both English and Marshallese. Marshallese recruitment staff will also give a presentation about the study at churches after religious services. While this method of recruitment may seem unconventional, we have successfully used it to engage the Marshallese community, and our CBPR group believes it is the most culturally appropriate way to recruit.

At targeted community and health events, we will set up a booth and provide informational materials as well as be available to discuss the study in more detail. If potential participants are interested in enrolling in the study, they will complete a form that captures contact information and a meeting will be set up so that the consent process can take place in private.

We will also provide a dedicated e-mail address and phone lines for any interested community members who hear about this study through community leaders, Marshallese Community Advisory Board members, and Yokwe.net to learn about and participate in the study.

**Participants and family member measures.** As discussed above, the participants assigned to the treatment group will be asked to invite between one and ten family members to join them for the education sessions. Family members may or may not have Type 2 diabetes. Family members will be provided the opportunity to consent after the initial participants have invited them to take part in the study. Primary analysis will be based on the participants with diabetes. In addition, we will collect and analyze the outcomes of the family participants who have consented and report any value added by including outcomes of family members. We will collect biometric and survey instrument data on family members who consent and participate. If family members are found to have elevated HbA1c during the data collection but have not previously been diagnosed with diabetes, we will refer them to a health care provider.

Primary participant's diabetes status will be confirmed by their HbA1c at the time of initial data collection. Primary participants who do not have HbA1c results indicative of diabetes, 6.5 or above, will be unenrolled from the study as primary participants. If they were randomized into the family arm of the study and another family member does have HbA1c results indicative of diabetes, participation of the entire family unit (including with an HbA1c less than 6.5) will continue.

## **Risks and Benefits**

Potential risks to study participants are minimal and no greater than usual care or standard health screenings. There is a potential risk for loss of confidentiality. Measures to protect the confidentiality of study participants will be implemented as described in the Data Handling and Recordkeeping section below.

Title: *Family Model of DSME in the Marshallese Community*

PI: *[name]*

The DSME has the potential to benefit participants by fostering better disease management activities and improving health and quality of life. In addition, knowledge gained from the study could impact future delivery of DSME to minorities and underserved populations.

## **Data Capture**

The study team will utilize an electronic database to capture study data. Survey instrument responses will be captured with paper and pencil instruments (PAPI). All surveys will be available in English or Marshallese and then entered into the database. A translator/interpreter will be available to assist participants. Biometric data will be collected and recorded in the database. Upon entry into the study, each participant will be assigned a participant identification number and registered to the study.

## **Data Handling and Recordkeeping**

The Principal Investigator will carefully monitor study procedures to protect the safety of research subjects, the quality of the data and the integrity of the study. All study subject material will be assigned a unique identifying code or number. Only study investigators and analytical and quality assurance staff will have access to the code and information that identifies the subject in this study. All hard copies of study materials will be kept in a locked file and the key to the participant codes and any electronic data will be stored on a secure, encrypted server.

## **Data Analysis**

### Sample size and power considerations

All of the power and sample size calculations and estimations were performed using PASS 2008 (NCSS, LLC. Kaysville, Utah. [www.ncss.com](http://www.ncss.com)). Our study design is a randomized two-group construct with 4 repeated time points (baseline, post intervention, 6 months, and 12 months). So at its core, the study is a two-factor design with repeated measures, which can be expanded into a general linear regression model, with main covariates being group assignment, time, their interaction, and adjustment for other covariates. The sample sizes will achieve 80% power to detect a medium effect of 0.3 in a design with 4 repeated measurements having a compound symmetry covariance structure. The correlation between observations on the same subject is assumed to be of moderate magnitude at 0.5, and the alpha level is 0.05. This hypothesized detectable effect is of the same magnitude as a study that reported approximately 0.5% change in HbA1c with the standard deviation of the change being 1.5%.

### Statistical Analysis

All of the analyses are going to be conducted using SAS v9.3 (SAS Institute Inc. Cary, NC. [www.sas.com](http://www.sas.com)). Preliminary analyses will include the generation of descriptive statistics and assessment of group differences at baseline, as well as examination of distributions, treatment drop-out, and missing data patterns' impact on treatment effects.

Title: *Family Model of DSME in the Marshallese Community*

PI: *[name]*

Comparison of baseline characteristics between the two groups are going to be performed using two sample techniques such as a two-sample t-test and chi-square test; however, if the distributional or other assumptions have been violated we are going to use non-parametric alternatives, like Wilcoxon Rank Sum test, and/or Fishers exact test. Additional statistical analyses and considerations follow.

#### Analysis of primary outcome

The primary outcome is change in HbA1c between baseline, post intervention, 6 months post-intervention, and 12 months post-intervention. Repeated measures of these outcomes will be obtained at four visits as described. Our primary analytic approach will use general linear models (GLM) and mixed models for continuous repeated measures to model the mean outcome differences and covariance structures between the groups. Using these models, group effects will be estimated and tested by comparing group-specific means at post intervention, 6 months, and 12 months, while conservatively adjusting for the baseline differences in ANCOVA like mixed regression models.

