### **Hypothesis and/or Specific Aims or Objectives**

We hypothesize that a culturally adapted DSME implemented in a family model will result in better diabetes management outcomes compared to traditional DSME for the Marshallese.

In the family delivery model, a participant is encouraged to invite his/her family members to the diabetes educational sessions. As outlined by stakeholders, the model has several potential benefits. First, patients are empowered to invite the people they define as family and as appropriate for taking part in the sessions with them. Second, the education will engage the patient-defined support unit. Third, given the high rate of diabetes within the community, it is highly probable that others within the group will have Type 2 diabetes or pre-diabetes and may benefit from the intervention as well.

Our aim is to test a Family Model of DSME using a mixed-methods approach. Marshallese participants with type 2 diabetes will be recruited. Those who are assigned to the family model will be asked to invite one to ten adult members of their families to participate in the DSME. Given that ~30-50% of adults in the Marshallese community have type 2 diabetes, and the Marshallese typically have large families, recruitment for this nontraditional model is plausible. Furthermore, the method was designed from input from our CBPR partnership with the Marshallese.

This research is highly translational. It will help bridge the gap between knowledge of an effective DSME intervention and actual implementation of the intervention among a Pacific Islander population with especially high rates of type 2 diabetes and significant health disparities.

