### **Study Design and Procedures**

We will conduct a comparative effectiveness evaluation using a randomized control trial design of the adapted Family Model of DSME, and compare results of the Family Model of DSME with traditional DSME within the Marshallese population. The family model will cover the same concepts as the traditional format. However, the family model will incorporate culturally-adapted education and recommendations aimed at engaging family members in the management of the primary participant's diabetes, and family members will be invited to fully participate in the study. By contrast, the traditional model provides diabetes self- management education to the diabetic participant only, and the participant's family members do not participate in the classes or any other part of the

Title: *Family Model of DSME in the Marshallese Community*

PI: *[name]*

study. Biometric and survey data will be collected pre-intervention, post-intervention, 6 months post-intervention, and 12 months post-intervention. In the event missing data is identified, participants will be contacted to collect the missing data. A qualitative debriefing session will be held for each family between the final DSME session and the 6 month post-intervention to obtain qualitative data regarding the participant's perceptions of the intervention and implementation process. Participants will be offered a \$20 gift card as compensation for their time for each biometric data collection event and the qualitative debriefing session.

**Randomized participant assignment.** Six cohorts will be recruited, approximately three months apart. Each cohort will be comprised of 75 participants with diabetes, with 50% being assigned to the Family Model arm and 50% being assigned to the traditional DSME control group. The study sample size will be the total of each cohort; thus a total of 300 diabetics and up to 2000 family members (only those in the family model arm will be inviting family members). We initially chose an unequal group design (70/30), but after assessing Cycle 1 attrition, we needed to adjust the ratio in order to have sufficient control group numbers for analysis. Discussion with stakeholders resulted in support for this modification. Each participant will be randomly assigned to a group after consent.

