#### Missing data

Analyses of our primary outcome variable (mean differences in HbA1c between groups) will be done in accordance with the intent-to-treat principle. That is, data from all randomized participants will be analyzed regardless of compliance with study protocol or failure to complete the study. For this reason, we propose to impute the missing data using SAS PROC MI and its inbuilt MCMC algorithm, which is the most appropriate imputation method for the arbitrary missing data mechanism. If the data are missing according to non-ignorable mechanism, alternative imputation mechanisms will be considered. Imputed data will be combined and analyzed using SAS PROC MIANALYZE in order to generate appropriate estimates and their standard errors.

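### The primary HbA1c analysis compares the arms at three visits without saying which comparison decides; if any visit may count, type I error is about 12.5% to 13.5% instead of 5%

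*Combined protocol and SAP*

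**What the plan says.** The section on analysis of the primary outcome defines the outcome over every visit: "The primary outcome is change in HbA1c between baseline, post intervention, 6 months post-intervention, and 12 months post-intervention". It then says that, from general linear and mixed models with baseline adjustment, "group effects will be estimated and tested by comparing group-specific means at post intervention, 6 months, and 12 months".

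The missing-data section refers to the same outcome without a visit: "Analyses of our primary outcome variable (mean differences in HbA1c between groups".

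The power section describes the design as a whole ("So at its core, the study is a two-factor design with repeated measures"), with group, time and their interaction as main terms. It gives one power statement, "The sample sizes will achieve 80% power to detect a medium effect of 0.3 in a design with 4 repeated measurements", and one error rate, "and the alpha level is 0.05". It does not say which term or contrast either figure belongs to, or whether tests are two-sided.

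The section on secondary outcomes speaks of group effects, time effects and their interaction, and says its methods are similar to those for the primary outcome. It does not name a deciding test.

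The hypothesis is directional but has no time point: the family model "will result in better diabetes management outcomes compared to traditional DSME for the Marshallese".

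**The concern.** A model with group, time and interaction terms offers several tests of the family model: a group effect averaged over visits, an interaction or joint test, and three visit-specific differences. The plan chooses none of them. The sentence on testing names three visits, so a reader who follows it literally makes three unadjusted primary comparisons.

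The effect of an education programme may well differ between the end of classes and a year later. Under this text, a difference just after the classes that is gone by 12 months could be reported as success on the primary outcome. So could the reverse pattern. A reader of the results could not tell whether the contrast was fixed beforehand.

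**Working it through.** **Inputs from the plan.** Alpha 0.05; compound symmetry over 4 measurements with correlation ρ = 0.5; effect 0.3; 80% power (all from the power section). Three post-baseline comparisons with baseline adjustment (primary analysis section). Total size: "thus a total of 300 diabetics" (study design section).

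**Assumptions.** Two-sided tests; effect in SD units; 150 per arm; for power, no dropout; no clustering by family. The 150 is an assumption because the same section also describes six cohorts of 75, which is 450.

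**1. The plan's 80%.** It cannot be reproduced, because the power section does not give the sample size, allocation or contrast behind it. With 150 per arm and effect 0.3, none of the contrasts tried gives 80% within 2 points (step 4).

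**2. Correlation between the three visit tests.**
- Baseline-adjusted: variance 1 − ρ² = 0.75 and covariance ρ − ρ² = 0.25, so r = 0.25/0.75 = 1/3.
- Change scores: variance 2(1 − ρ) = 1 and covariance 1 − ρ = 0.5, so r = 0.5.

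**3. Type I error if any visit counts.** For three equicorrelated standard normals with no true effect, by numerical integration:

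| Rule | r = 1/3 | r = 0.5 | One test |
|---|---|---|---|
| Any \|z\| > 1.96 | 13.5% | 12.5% | 5% |
| Any z > 1.645 (one-sided 0.05) | 12.9% | 11.8% | 5% |
| Any z > 1.96 (favours family model only) | 6.8% | 6.3% | 2.5% |
| Any \|z\| > 2.394 (0.05/3 per visit) | 4.7% | 4.5% | – |

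Independent tests would give 1 − 0.95³ = 14.3%. Correlations above those the plan implies give less: 10.9% at 0.7, 9.8% at 0.8 and 8.4% at 0.9. A single test, whether of the three-visit average or a joint 3-df test, keeps 5%.

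**4. Power by contrast.** For a single mean contrast with variance factor v, power = Φ(0.3/√(2v/150) − 1.96).

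| Contrast | v | Power |
|---|---|---|
| One visit, change score | 1 | 74% |
| One visit, baseline-adjusted | 0.75 | 85% |
| Average of three post visits, unadjusted | 0.667 | 89% |
| Average of all four visits | 0.625 | 91% |
| Average of three post visits, baseline-adjusted | 0.4167 | 98% |
| Joint 3-df test, baseline-adjusted (noncentrality 16.2) | – | 94% |

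Here 0.4167 = (0.75 + 2 × 0.25)/3.

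**5. Sensitivity to sample size.** If the first cohort was split 53 to 22, as the milestones table has it, and the remaining 225 equally, the arms are 165.5 and 134.5. The change-score, baseline-adjusted single-visit, baseline-adjusted average and joint-test figures then move by less than 1 point. With 225 per arm, baseline-adjusted power at one visit is 96%. With the completers in the milestones table (53 + 110 = 163 and 22 + 50 = 72) it is 69%.

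**The case against.** The strongest reply is that the plan never says any visit may count. One alpha, one repeated-measures design and a secondary-outcome section written in terms of group, time and interaction effects all suggest one model-level test, with error 5%. This reading is possible, and it is why the inflation is conditional. It does not close the gap, because the sentence that describes testing names three visits and the plan never says which model term decides.

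Further points stand as refinements:

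- The group-by-time interaction is another candidate. With baseline kept as one of the four measurements, it is a 3-df test of differential change and also keeps 5%. That adds to the open choices.
- The hypothesis is directional, so 6.3% to 6.8% against 2.5% is the closer measure of a false claim for the family model. It is still more than double.
- Compound symmetry is a planning assumption only. If visit tests correlate at 0.8 or 0.9, the rate is less than doubled, but it remains above nominal.
- Families are randomised, and the primary analysis mentions no family term. Under an assumed design effect of 1.10 that the analysis ignores, even one test would have about 6.2% error. The 5% for a single test therefore presumes that clustering is handled.
- The 80% power is unclear for a second reason, the sample size. Naming the contrast is necessary to check it, but not sufficient.

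**Conclusion.** The concern holds. The primary analysis leaves the deciding comparison open, and the text taken literally gives three unadjusted primary tests. The defect is the open choice, not a stated any-visit rule.

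If any visit may count, type I error is 12.5% to 13.5% under the plan's correlation of 0.5 and two-sided tests, instead of 5%. Stated power cannot be linked to a test, since candidate contrasts differ by up to 24 points (98 − 74) on identical assumptions. The matter affects the main claim of the trial and should be corrected. It is not fatal, because a reading that keeps 5% exists and the repair is small.

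**What to change.** In the section on analysis of the primary outcome, name one primary contrast from the baseline-adjusted repeated-measures mixed model, tested two-sided at 0.05, and make the other visit comparisons secondary. Any one of these would do:

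- **Average** group difference over the three post-baseline visits. Power is 98% for a steady effect, but about 27% if 0.3 is present at one visit only (mean effect 0.1).
- **Joint test** of the three group differences. Power is 94% and 80% in those two cases. A significant result does not by itself show the direction or the visit, so direction must be read from the visit estimates.
- **One named visit**, such as 12 months if the claim is about a lasting effect. Power is 85%, and an effect elsewhere is missed.

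If all three visits are to be primary, use Holm. Power at a given visit then falls from 85% to no less than about 73% (the first step, at 0.05/3). With a steady effect it is about 81% per visit, and about 94% for at least one visit.

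These prices assume 150 per arm, no dropout and no clustering.

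In the power section, state which contrast, sample size and allocation the 80% refers to. The cost is one or two sentences in the first section and one in the second, with no extra data. Under any single-contrast option, the remaining visits lose primary status.
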